Besides being the most comprehensive and best validated neuropsychological test battery for diagnostic purposes, the expanded HRB is finding increasing use in predicting the problems that neurologically impaired patients have in their everyday functioning (Denerll, Rodin, Gonzalez, Schwartz and Lin, 1966; Schwartz, Denerll and Lin, 1968; [name], Chelune, and Lehman, 1977; Newnan, [name] and Lehman, 1977). Therefore, the use of this test battery will enhance the possibility of correlating changes in neuropsychological functioning with changes in quality of life in COPD patients.

In a pilot study conducted in the Neuropsychology Laboratory at the University of Colorado Medical Center, it was determined that the expanded HRB took four to six hours to administer to COPD patients. All patients tolerated the testing well, and were able to complete it in a single testing session (given periodic breaks and time out for lunch, of course).

The Repeatable Battery has been added to the study protocol in order to determine more precisely when treatment-induced neurologic changes occur. There are two main advantages to this Battery: first, it takes less than an hour to administer; and they can be re-administered at short intervals without having practice effects influence the results. Also, the sensitivity of the Repeatable Battery to drug-induced changes in CNS functioning has been demonstrated in previous research (e.g., Rennick, Keiser, Rodin, Rim and Lennox, 1974; Lewis, Rennick, Clifford, Rodin and Rim, 1976). The disadvantages of the Repeatable Battery are that it covers a restricted range of abilities (general alertness, attention,

flexibility of thinking, and motor speed and coordination) and that it is relatively new and has not yet been shown sensitive to cerebral pathology involving many etiologies. Nevertheless, used in conjunction with the expanded HRB, this battery may help determine not only the types and degrees of treatment-induced behavioral changes, but also the time it takes for such changes to occur. The following are tests included in the abbreviated Repeatable Battery (brief descriptions are provided only for tests not described in Reitan and Davison, 1974 or Wechsler, 1955):

Digit Symbol. This is abstracted from the Wechsler Adult Intelligence Scale, and has six alternate forms.

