Color Naming. This uses a test booklet containing a series of 48 sets of four colored squares which must be correctly named by the subject in sequence. Total time and errors are recorded. (See Goldstein, 1973).

Grip Strength. Grip strength with both hands is measured with the Smedley Hand Dynamometer (Lafayette Instrument Company).

Grooved Pegboard. See Reitan and Davison, 1974.

Finger Oscillation Test. See Reitan and Davison, 1974.

Trail Making Test (Part B). See Reitan and Davison, 1974. Five alternate forms of this test are available.

Sentence Writing Time. This is a test of motor speed and coordination in a familiar but complex activity. The subject is asked to write the sentence "The large dog runs fast" with the dominant hand. The sentence is presented verbally as well as visually on a 3x5 card. There are three trials, and the times from the last two trials are averaged to compute the subject's score.

Visual Search. This is a measure of elementary visual pattern matching under conditions of high visual noise. Subjects are asked to match a small checkerboard-like pattern to another one like it found in a highly redundant array of similar patterns. Eight presentations

4-2449

are made from the test booklet and total time and errors are recorded. There are two alternate forms.

Discrimination Reaction Time Test-Substitute. This replaces the original computer assisted test and provides a measure of sustained attention and discrimination speed. The subject is asked to cross out a specific number, six or nine, which appears randomly within 61 rows of 35 single digits. Each number is equally and randomly presented enabling repeated administrations with different numbers. Total time and errors are recorded.

The Repeatable Battery will be administered to each patient four times before oxygen therapy is instituted. The first three administrations constitute the training trials, and the fourth provides the baseline measures. Each patient will then be readministered the Repeatable Battery after one, two, three and six months of oxygen therapy.

Neuropsychiatric History Questionnaire. The NOTT is a study concerned with the neuropsychological concomitants of COPD and potential cognitive benefits of two forms of oxygen treatment--continuous and nocturnal.

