Once a subject with the proper demographic characteristics has been identified and willingness to participate is ascertained, a "normal comparison group screening questionnaire" will be completed. This screening procedure will assure that the comparison subjects are in good general health, do not have COPD, and do not have other illnesses (e.g., alcoholism, psychosis) which might interfere with neuropsychological testing. Records will be maintained on the number of attempts to contact a prospective subject, number of refusals, number of rejections because of violation of screening and dropouts. (See case finder tally sheet.)

PROCEDURES

A. Neuropsychological Assessments

The Halstead-Reitan Battery including the Modified Wechsler Memory Scale Wechsler Adult Intelligence Scale and the Minnesota Multiphasic Personality Inventory (MMPI) will be administered to these subjects. Additionally, those tests of the Lafayette Repeatable Battery which are not in common with the Halstead-Reitan will be administered once. In effect this will mean that there will be a complete Halstead-Reitan and one complete Lafayette Repeatable on each comparison subject at each testing occasion (see below).

B. Quality of Life Measures

The Sickness Impact Profile (SIP) and the Profile of Mood States (POMS) will also be administered.

C. Neuropsychiatric Interviews

The initial neuropsychiatric history with both its medical and substance use (including tobacco) components will be administered to each subject.

D. Timing of Psychological Assessments

Each comparison subject will be examined on two occasions. The second examination will be twelve months after the initial examination. Procedures A, B, and C above will be repeated at the second examination with the exception that the neuropsychiatric interview form will be modified to cover the preceding six months only.

E. Data Processing

All data will be forwarded to the Neuropsychology Screening Centers in the same manner as the neuropsychology data collected by the study protocol.

F. Subject Fees

For their time, each participant may be paid \$25.00 at each occasion.

G. Informed Consent

Informed consent will be obtained. A sample consent document approved by UCSD's Committee on Investigation/Activities Involving Human Subjects is attached for your information.

IPPB Patient

Neuro-)ch

Halstead-

Reitan X

X

MMPI X

X

Lafayette X

X

Quality
of Life

SIP X

X

X

X

X

KAS-R X

X

X

X

X

POMS X

X

X

X

X

RLCQ X

X

X

X

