The purpose of this meeting was to determine those neuropsychological and quality of life variables which would be utilized in making decisions regarding the length of the NOTT follow-up period. A complete analysis of those selected variables would be presented to a subcommittee of the Advisory Board in February and, subsequently, to the full Advisory Board in March. Such an analysis would include an assessment of treatment differences, statistical power calculations, as well as projected conclusions that would be made at the scheduled end of the NOTT study. It was decided that no more than twenty variables should be considered for this purpose.

After considerable discussion the following variables were selected:

Rennick Repeatable Battery:

(1) Percent Tests Impaired - This variable is calculated as the percent of nine tests on which a given individual is impaired. For the purposes of power calculations, a five percent difference in mean values for the 12 hour and 24 hour treatment groups would be considered clinically important.

(2) Average Impairment Rating - For the purposes of power calculations, a .10 difference in mean values for the 12 hour and 24 hour treatment groups would be considered clinically important.

NOTE: The baseline values for the above two variables will be determined from the last administration of the Rennick Repeatable Battery before randomization. If less than three administrations are available, the baseline results will be considered to be missing. Since the Rennick Repeatable Battery is administered at baseline, 1, 2, 3, and 6 months, a multivariate analysis will be utilized comparing the two treatment groups with respect to their average response at these five time points. However, attention will be focused at a comparison of the linear trend over time for the two groups. If it is necessary to reduce the number of variables for consideration, the average impairment rating may be omitted.

Halstead-Reitan Battery:

(1) Russel-Neuringer-Average Impairment Rating - For the purposes of power calculations, a .10 difference in mean values for the 12 hour and 24 hour treatment groups would be considered clinically important.

(2) Impairment Index - This index is based on eight scores. For the purposes of power calculations, a .05 difference in mean values for the 12 hour and 24 hour treatment groups would be considered clinically important.

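### The protocol conflicts on how often IPPB patients take the Repeatable Battery before baseline; if training trials apply to patients only, the comparison with controls is confounded with practice

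*Protocol*

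**What the plan says.** Three parts of the protocol bear on how often the Repeatable Battery is given.

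- **I. Background, Neuropsychological Evaluations.** "The Repeatable Battery will be administered to each patient four times before oxygen therapy is instituted". The next sentence fixes the score: "The first three administrations constitute the training trials, and the fourth provides the baseline measures". Retests follow at one, two, three and six months of oxygen therapy. The same section commends the battery because "they can be re-administered at short intervals without having practice effects influence the results".
- **II. Patient Study, B. Testing.** For IPPB patients the Lafayette battery appears once at baseline and once at twelve months, with no neuropsychological testing at six months. Training trials are not mentioned. A footnote treats the Lafayette and Rennick batteries as essentially the same.
- **III. Control Study, Procedures A and D.** For controls, "those tests of the Lafayette Repeatable Battery which are not in common with the Halstead-Reitan will be administered once", so that "there will be a complete Halstead-Reitan and one complete Lafayette Repeatable on each comparison subject at each testing occasion". On timing, "Each comparison subject will be examined on two occasions", twelve months apart.

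The case-finding conference summary (I. Introduction) gives the purpose of the control sample: a healthy group against which to compare the patients' neuropsychological functioning.

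**The concern.** A comparison of patients with healthy controls on a performance test is clean only if both groups meet the test with the same experience of it. Under the Background text the patient's baseline score is a fourth attempt. Under the Control Study text the control's is a first attempt. If scores improve over early attempts, part of the patients' deficit is offset by rehearsal and COPD-related impairment looks smaller than it is. This is a bias, so enrolling more subjects would not reduce it.

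The protocol leaves open whether this will happen. A center that follows the Background will train its patients; a center that follows the Patient Study schedule will not. With two centers contributing 50 patients each, both practices could occur in one data set.

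**Working it through.** **1. Exposure counts under each reading** (Repeatable Battery as a whole)

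| Reading | Patient at baseline | Control at first occasion | Patient at 12 months | Control at 12 months |
|---|---|---|---|---|
| Patient Study schedule | 1st | 1st | 2nd | 2nd |
| Background pre-treatment trials, then Patient Study follow-up | 4th | 1st | 5th | 2nd |
| Background in full (4 + 4 retests + 1) | 4th | 1st | 9th | 2nd |

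The first row is balanced. The other two are not.

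**2. Shared tests.** Controls take tests common to both batteries once per occasion. If patients meet these tests in the Halstead-Reitan and again in four Repeatable Battery administrations, they have up to 1 + 4 = 5 exposures by the end of baseline. Digit Symbol is one such test, since the protocol takes it from the Wechsler scale that it adds to the Halstead-Reitan.

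**3. Does the document rule out a practice gain?** It asserts that there is none, yet sets aside three administrations as training, which makes sense mainly if early attempts differ from later ones. Of the nine tests listed, alternate forms or targets are described for four: Digit Symbol (six forms), Trail Making B (five), Visual Search (two) and the reaction-time substitute (different target digits). Four administrations with two Visual Search forms must reuse a form. No alternate forms are described for Color Naming, Grip Strength, Grooved Pegboard, Finger Oscillation or Sentence Writing. The assertion is therefore doubtful, but no gain is quantified.

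**4. Scale of a possible bias.** The plan gives no power, SD or practice gain for this comparison, so there is no figure to reproduce. Inputs from the protocol are 50 + 50 = 100 patients and 15 + 15 = 30 controls. Assumptions are a common SD of 1, independent groups, two-sided alpha 0.05, and a practice gain g from 0 to 0.5 SD.

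SE = sqrt(1/100 + 1/30) = 0.208 SD

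Bias in standard errors = g / 0.208:

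- g = 0: 0
- g = 0.2: 0.96
- g = 0.5: 2.4

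**5. What that does to inference** (illustration). The expected observed impairment is d − g, where d is the true impairment. The chance of showing it is Φ((d − g)/0.208 − 1.96). With no true impairment, the chance of a significant difference is Φ(g/0.208 − 1.96) + Φ(−g/0.208 − 1.96).

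| g (SD, assumed) | 0 | 0.1 | 0.2 | 0.3 | 0.5 |
|---|---|---|---|---|---|
| Power, d = 0.6 | 0.82 | 0.67 | 0.49 | 0.30 | 0.07 |
| Power, d = 0.8 | 0.97 | 0.92 | 0.82 | 0.67 | 0.30 |
| Significant difference when d = 0 | 0.05 | 0.08 | 0.16 | 0.30 | 0.67 |

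For g above zero, the excess in the last row over 0.05 consists of results that make patients look better than controls.

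**The case against.** The strongest reply is that the four-administration text does not belong to this trial. It is tied to oxygen therapy, and the paragraph after it describes the NOTT, a study of continuous and nocturnal oxygen. The section written for IPPB patients lists one baseline administration, and on that reading exposure is equal and the problem disappears. This stands as a limit on the claim. It does not dispose of it, because the Background introduces both batteries as those to be used in the IPPB study. The Patient Study list names instruments by time point and does not say how many trials make up a baseline.

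A second reply is that the battery is declared free of practice effects. If so, there is no bias. The training trials and the incomplete set of alternate forms make that an unsafe assumption, but nothing in the document shows that a gain exists or how large it is.

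A third reply is that the Repeatable Battery was added to time treatment-induced change, and that the Halstead-Reitan supplies the summary impairment scores. That limits the reach: Halstead-Reitan tests outside the shared set, the MMPI and the quality of life measures are not affected by the training trials.

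A reader might also infer from the NOTT minutes, "If less than three administrations are available, the baseline results will be considered to be missing", that every control baseline would be void, since controls have one administration. The documents do not support this: the rule concerns the last administration before randomization in a comparison of two oxygen groups, and controls are not randomized. Likewise, the five-point difference in Percent Tests Impaired in those minutes is a NOTT treatment-group criterion and is no yardstick for patient-control bias.

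**Conclusion.** The protocol contradicts itself on how many times IPPB patients take the Repeatable Battery before baseline, and the passages must be reconciled. If the Background's training trials apply to patients and not to controls, the comparison on this battery and on the shared tests is confounded with practice, in a direction that tends to understate impairment. Given 100 patients, 30 controls, equal SDs and an assumed gain of 0 to 0.5 SD, the bias is 0 to 2.4 standard errors. The upper end would matter greatly; the lower end is no bias at all.

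A reader might go further and conclude that the comparison is biased and hides COPD-related impairment. The documents do not establish that. They leave open which schedule governs and give no practice gain, and a small gain would weaken a real difference without concealing it.

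**What to change.** 1. Reconcile Background, Patient Study B and Control Study Procedures A on the number of Repeatable Battery administrations before baseline, for IPPB patients and for controls. Say explicitly whether the oxygen-therapy schedule applies to IPPB.
2. If training trials are kept for patients, require that first-administration scores be recorded and retained. The protocol does not say that they are, and scores not recorded at first testing cannot be recovered.
3. Base every baseline patient-control comparison on equal exposure: first administration against first and, for tests shared with the Halstead-Reitan, the earliest score in each group, whichever battery it came from. List the shared tests.
4. Use the fourth administration only for comparisons between treatment groups.
5. Do not compare twelve-month levels or changes with controls on the Repeatable Battery or the shared tests unless exposure counts match. Use the non-shared Halstead-Reitan tests for that purpose.

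The cost is a few sentences of text and retention of scores from sessions that would take place anyway. The drawback is that first-trial scores are somewhat noisier than trained ones. If the reconciliation shows that IPPB patients have a single baseline administration, steps 2 to 5 fall away.

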It is important to account for known sources of variability in neuropsychological results in order to partial out the unique effect(s) of COPD and oxygen therapy. Past medical history is known to affect neuropsychological test findings. It is evident that persons with histories of neurological disorder (head injury, learning disability, stroke, diabetes with arteriosclerotic vascular disease, encephalitis, etc.) are at greater risk to show neuropsychological deficit than are persons without such histories. For this reason, a detailed medical-neurological history is essential. Our prediction is that a proportion of the variability in neuropsychological findings will be accounted for by medical history.

It is also known that alcohol abuse relates to neuropsychological deficit (see attached review by [name] and Mohns (1974) of chronic cerebral effects of alcohol and drug abuse). Recent evidence ([name] et al., 1976; [name] and Judd, 1976; [name] et al. 1977) has also implicated heavy use of other drugs, particularly CNS depressants, in neuropsychological impairment. This relationship was found in heavy drug users who were, however, very youthful, suggesting that the effect might be a potent one. For these reasons we must be sure that observed impairment in pulmonary patients is not a product of alcohol/drug use, acute or chronic. Our prediction is that, in persons with substantial alcohol/CNS depressant drug use, a proportion of the

variability in impairment will be accounted for by substance use history.

The neuropsychiatric history proposed here is a modification of one used in a recent national collaborative polydrug study. Neither version is copyrighted. Extensive validity-reliability studies were not possible in the collaborative polydrug study. Nevertheless, the following information exists:

1. The interim drug use questionnaire correlated significantly with toxicological examinations of blood and urine ($p < .01$). This is one measure of concurrent validity.
2. Both medical and drug use information contributed significantly to NP findings, suggesting its validity (usefulness).

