 - ii. HAPI
 - iii. Lafayette "Repeatable Battery" *
- b. Quality of Life measurements
 - i. SIP
 - ii. KAS-R
 - iii. POMS
 - iv. Recent Life Changes Questionnaire (RLCQ)

2. Six Month Anniversary

- a. Neuropsychological Testing - none
- b. Quality of Life
 - i. SIP
 - ii. KAS-R
 - iii. POMS

3. Follow-up

- a. Neuropsychological Testing (twelve months)
 - i. Modified Halstead-Reitan
 - ii. HAPI
 - iii. Lafayette "Repeatable Battery"
- b. Quality of Life (12, 24, and 36 months)
 - i. SIP
 - ii. KAS-R
 - iii. POMS
 - iv. RLCQ

C. Data Processing

All completed Quality of Life forms go directly to the Data Center ([name]). Neuropsychological forms are reviewed in Oklahoma ([name]) and then go to the Data Center ([name]).

*Lafayette and Rennick "Repeatable Batteries" are essentially the same.

III. CONTROL STUDY

A. Sample Size

Thirty subjects will be recruited (15 at Oklahoma and 15 at Winnipeg).

B. Subject Selection

It will be important that the normal comparison group provide a match to the IPPB patients in terms of certain demographic characteristics. To ensure this, [name] at the George Washington Data Center will provide each study center with a description of the kind of normal controls that should be recruited. The Data Center will specify criteria ranges for age, education and sex. Your case finder should call Bethesda to obtain a list of case numbers drawn from your COPD subject pool.

C. Subject Recruitment

There are many ways in which a comparison group might be selected. The Advisory Board to IPPB studies has determined that a "neighborhood control" approach would be appropriate. In brief, this approach involves: 1) identifying the neighborhood from which a typical patient comes and 2) employing a predetermined procedure in searching the neighborhood for a normal comparison subject to match that patient.

The details of the searching procedure have been worked out. Your case finder has been trained in their application and a complete summary of the method has been attached.

D. Screening Subjects

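### The controls' repeat neuropsychiatric interview looks back six months over a twelve-month interval, so an event confined to the first half is asked about at neither interview

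*Protocol*

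**What the plan says.** Protocol section III (Control Study) sets the size of the group: "Thirty subjects will be recruited (15 at Oklahoma and 15 at Winnipeg"). Under Procedures, D (Timing of Psychological Assessments), "Each comparison subject will be examined on two occasions", and "The second examination will be twelve months after the initial examination". The same paragraph repeats the tests, the quality-of-life measures and the neuropsychiatric interview at the second visit, except that "the neuropsychiatric interview form will be modified to cover the preceding six months only".

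Procedures, C describes the interview at the first visit: "The initial neuropsychiatric history with both its medical and substance use (including tobacco) components will be administered to each subject". The control schedule chart shows the History row marked at the two examinations only.

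The reason for taking a history is in section I (Background), under Neuropsychiatric History Questionnaire: "Past medical history is known to affect neuropsychological test findings". After listing conditions such as head injury and stroke, the text concludes: "For this reason, a detailed medical-neurological history is essential". It gives a parallel argument for alcohol and CNS-depressant drugs.

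**The concern.** The look-back does not fit the interval. The first interview covers the time up to the initial examination, and the second covers months 7 to 12 after it. Months 1 to 6 belong to neither.

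The controls are meant to be a healthy comparison sample for the patients' neuropsychological functioning, and section II.B.3 retests the patients at twelve months as well. Suppose a control has a head injury or stroke in month 3 that still affects performance in month 12. The planned questions would not bring it out, and the poorer second result would stand among the normal ones. That would tend to make a decline in patients look less unusual. An analysis plan cannot repair this, because the information would not have been collected.

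**Working it through.** The protocol states no figure on this point, so there is none to reproduce. The check has three parts.

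**1. Coverage (inputs from section III.A and Procedures, D).**
- Uncovered window = interval − look-back = 12 − 6 = 6 months, and 6/12 = 50% of the interval.
- With 30 controls and no dropout: 30 × 6 = 180 of 30 × 12 = 360 control person-months.

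**2. Does anything else in the protocol close the gap?**
- *Another control contact:* none is listed between the two examinations.
- *Health screen (III.D, Screening Subjects):* "This screening procedure will assure that the comparison subjects are in good general health, do not have COPD, and do not have other illnesses". It is completed before enrolment, and no repeat is stated.
- *Repeated SIP and POMS:* they measure sickness-related dysfunction and current mood. They are not event histories.

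Nothing closes it.

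**3. Possible size.** The documents give no event rate, so the annual rate *r* of a relevant event is an assumption, shown over a range. Events are spread evenly over the year.
- Probability of an event in the uncovered half: p = 1 − (1 − r)^0.5.
- Expected number of controls affected: 30p.
- Chance of at least one: 1 − (1 − p)^30 = 1 − (1 − r)^15.

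| Assumed r per year | Expected controls affected | Chance of at least one |
|---|---|---|
| 2% | 0.30 | 26% |
| 5% | 0.76 | 54% |
| 10% | 1.54 | 79% |
| 20% | 3.17 | 96% |

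The simple approximation 30 × r × 0.5 gives nearly the same counts: 0.75 at 5% and 1.5 at 10%.

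Shift in the mean control change, in SD units of change:
- One control declining by 1 SD (assumed): 1/30 = 0.033 SD.
- Expected shift at 5%: 0.75 × 1/30 = 0.025 SD. At 10%: 1.5 × 1/30 = 0.05 SD.
- Less favourable case, two controls declining by 2 SD each: 2 × 2/30 = 0.133 SD.

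Standard error of a mean change in 30 controls: 1/√30 = 0.183 SD. The expected shift is therefore 0.025/0.183 = 14% to 0.05/0.183 = 27% of one standard error.

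**After the change:** 12 − 12 = 0 months uncovered, and 0 of 360 person-months.

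**The case against.** The mismatch itself is not in dispute. The case on the other side concerns what follows from it.

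- **A reader might infer that the gap contaminates the normal reference.** The documents do not show this. It needs a relevant event in the first half of follow-up with an effect that lasts to month 12. These controls are screened for good health and against illnesses such as alcoholism and psychosis, and the event rate and the 1 SD decline are both assumptions. Even on those assumptions the expected shift is well inside one standard error. This objection stands.
- **A reader might infer that everything in months 1 to 6 goes unrecorded.** That is too strong. Continuing illness or substance use can still be reported for months 7 to 12, and an event that has fully resolved need not affect the retest. The modified form is not shown, so its handling of ongoing conditions is unknown. This stands and narrows the loss to discrete events with lasting effect and nothing reportable later.
- **A reader might infer that the controls' twelve-month change is the defined yardstick for retest and ageing.** The protocol calls them a comparison group and tests them twice, which makes such use plausible. It specifies no change-score analysis, and no exclusion or adjustment for interval events. This stands. Nor do the controls enter any comparison between patient treatment groups, which is unaffected.
- **Better control history need not give a cleaner comparison.** Neither the patient testing list in II.B nor the patient chart shows a neuropsychiatric history; only the control chart has that row. Dropping controls with interval events while keeping similar patients would create an imbalance in the other direction. This stands and limits how the information should be used.

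None of these points supplies a reason for a six-month look-back over a twelve-month interval.

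**Conclusion.** The point holds as a mismatch between two stated rules. It is an error in what the protocol fixes, not detail left to an analysis plan. Confidence is high for the coverage gap, which rests only on the protocol's own intervals.

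The consequence is modest and conditional. A control with a discrete event in about the first six months and a lasting effect might not be recognised as such at twelve months. The 0.025-0.05 SD estimate rests on an assumed 5-10% annual event rate and an assumed 1 SD decline per case, with all 30 controls retained. It illustrates scale and does not demonstrate bias. The case for acting is that the protocol itself regards this history as essential, the missing half cannot be recovered by analysis, and the correction is very cheap.

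**What to change.** In section III, Procedures, D, and on the modified interview form, replace the six-month limit with *the period since the initial examination (twelve months)*.

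Use the added information to describe the controls or in a sensitivity analysis. Do not use it as a ground for excluding controls alone while the patient schedule lists no matching history.

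The cost is one phrase in the protocol and on one form, with no extra visit. The downside is a somewhat longer recall period, so events early in the interval may be reported less accurately than recent ones.
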